#### **10.2.2 Site Requirements for Reporting Serious Adverse Events to HCRN**

Site investigators and other site personnel must report any SAEs occurring from the time of informed consent to 30 days after the last dose of study drugs. This includes events both related and unrelated to the study drugs.

The definition of “related” being that there is a reasonable possibility the drug caused the adverse experience.

Unrelated	The Adverse Event is clearly not related to the study drug(s)
Unlikely	The Adverse Event is doubtfully related to the study drug (s)
Possible	The Adverse Event may be related to the study drug (s)
Probable	The Adverse Event is likely related to the study drug (s)
Definite	The Adverse Event is clearly related to the study drug (s)

The completed SAE Submission Form (see SPM) must be sent to HCRN **within 24 hours** of discovery of the event. The form may be sent to HCRN either electronically to [[contact]](mailto:[contact]) or by fax to [contact]. The site investigator is responsible for informing the IRB and/or the Regulatory Authority of the SAE as per local requirements.

The original copy of the SAE Submission Form and the fax confirmation sheet/email must be kept within the site study file.

Follow-up information should be submitted to HCRN either electronically to [[contact]](mailto:[contact]) or by fax to [contact], using a SAE Submission Form stating that this is a follow-up to the previously reported SAE and providing the follow-up number if appropriate. Each re-occurrence, complication, or progression of the original event should be reported as a follow-up to that event regardless of when it occurs. The follow-up information should describe whether the event has resolved or continues, if and how it was treated, and whether the subject continued or withdrew from study participation.

#### **10.2.3 HCRN Requirements for Reporting Serious Adverse Events to Bayer**

HCRN will report all SAEs to Bayer **within 24 hours** of receipt of the SAE Submission Form from the site and to regulatory authorities (FDA) per federal guidelines.

HCRN will report SAEs using a MedWatch form available at <http://www.fda.gov/medwatch/> for SAEs reportable to FDA; all other SAEs will be reported using the HCRN SAE Submission Form. All SAE reports must include the following minimum information:

1. The name and contact information of the reporter
2. The name of the study drug(s)
3. A description of the reported SAE

4. A subject identified by one or more of the following:
  - a. Subject initials
  - b. Subject number
  - c. Knowledge that a subject who experienced the adverse event exists
  - d. Age
  - e. Sex
5. An investigator assessment of study drug causality. For studies with combination therapy, a separate causality assessment should be provided for each study drug.

Additional data which would aid the review and causality assessment of the case include but are not limited to:

- The date of onset
- The severity
- The time from administration of study drug(s) to start of the event
- The duration and outcome of the event
- Any possible etiology for the event
- The final diagnosis or syndrome, if known
- Action(s) taken, if any

All reports shall be sent electronically to:

**Electronic Mailbox:** [[contact]](mailto:[contact])

**[contact]

**Address:** Global Pharmacovigilance - USA

**Mail only:** Bayer HealthCare  
[name]  
[name]

**Address:** [name]

**FDX or UPS only** [name] for UPS

#### **10.2.4 Expedited Reporting of Other Safety Information:**

Sites will report to HCRN **within 24 hours** of discovery of event and HCRN shall report to Bayer **within 24 hours** of receipt of report:

- An adverse event related to study specific procedures which the site investigator reasonably believes impacts subject safety (For Non-SAEs: site investigator decision whether to file to Bayer and other regulatory authorities).
- Any new and important event related to treatment with the study drug(s) which the site investigator reasonably believes impacts subject safety (this is up to the site investigator to determine what is new and important and related to the study drug. Site investigator decision whether to file to Bayer and other regulatory authorities).

- Any pregnancy during which a female patient was exposed to the study drug(s).  
Any pregnancy in the partner of a male subject, where the male subject was exposed to study drug at the time of conception or conception occurred within two weeks of the last dose of study drug(s).

Any communication, other than communication provided by Bayer, concerning safety related information to regulatory authorities or ethics committees including but not limited to:  
Development Safety Update Reports (DSUR) / relevant parts of IND reports for study drugs.  
Any other safety related reports, issues and queries that are either raised by or communicated to regulatory authorities or ethics committees.

#### **10.2.5 HCRN Reporting to the Food and Drug Administration (FDA)**

HCRN will manage the Investigational New Drug Application (IND) associated with this protocol on behalf of the sponsor-investigator. HCRN will cross-reference this submission to the IND (73,088) sponsored by [name] MD at Mayo Clinic.

For protocols conducted under an IND, HCRN will be responsible for all communication with the FDA in accordance with 21CFR312 including but not limited to the 7 and 15 Day Reports, as well as an Annual Progress Report.

#### **10.2.6 IND Safety Reports Unrelated to this Trial**

IND safety reports not occurring on this trial but involving the trial treatment (outside SAEs) received from Bayer will be forwarded to participating sites for submission to their Institutional Review Boards per their guidelines. IND safety reports will also be available in HCRN electronic data capture system.

## **11 STATISTICAL CONSIDERATIONS**

### **Power/Sample Size:**

The pilot study will enroll 90 total subjects and randomize them using a 2:1 allocation with 60 subjects enrolled in the Regorafenib + Ginseng group and 30 enrolled in the regorafenib + no ginseng group. The sample size is calculated based on the MFSI-SF fatigue endpoint. Based on the data published in Barton et al (2013), the expected standard deviations for the outcome of interest are 27.0 for the Ginseng group and 26.1 for the no ginseng group. Using a two group Satterthwaite t-test with a 0.050 two-sided significance level, there is 80% power to detect a difference between groups if the change in the no ginseng group is 10 and the change in the Ginseng group is 27 (or greater) (a group difference of 17 units). In addition, with this sample size, a two-sided 95.0% confidence interval for the difference of the two means (change in fatigue score for Ginseng group vs. change in fatigue score for no ginseng group) will extend 11.833 from the observed difference in means, assuming that the common standard deviation is 27.0 (conservatively choosing the standard deviation from the Ginseng group since it is larger than the no ginseng standard deviation) when the sample sizes are 60 and 30 respectively (a total sample size of 90) and the confidence interval is based on the large sample z statistic.

Based on previous published data [1] we believe that the Ginseng mean change in fatigue score will likely be closer to 20 (rather than 27); thus, we do not anticipate that this trial will reach

statistical significance. However, we will be able to refine our estimate of the standard deviation for the fatigue score in this subject population and provide a 95% confidence interval to estimate the likely boundaries for the true effect size. This information, along with estimates of retention and adherence, can be used to determine the sample size for further evaluation.

Furthermore, if the observed difference between groups is 12 or larger then this trial will provide both statistically significant and clinically meaningful evidence that Ginseng can help reduce fatigue in subjects taking regorafenib and a follow-up trial would not be needed. If the observed difference between groups at the end of the trial is 8-12 (expected difference based on previous study of Ginseng's impact on fatigue), then this study will have provided strong support for the potential efficacy of Ginseng and the follow-up trial designed to detect an effect of that magnitude would be justified. If at the end of this trial the observed difference between groups is close to zero then this would provide evidence to suggest that the potential beneficial effects of Ginseng may be less than expected and would warrant further discussion about whether a future trial should be performed.

### **Analyses:**

The primary objective is to assess the effect of Ginseng on fatigue using the multidimensional Fatigue Symptom Inventory–Short Form (MFSI-SF) and PROMIS Short Form v1.0 – Fatigue 8a. Subjects will have fatigue assessed at baseline and at weeks 2, 4, and 8. Repeated measures analysis of covariance will be used to assess the effect of Ginseng on fatigue. An unstructured covariance matrix will be used initially to account for the within subject correlation in fatigue over time. Additional covariance structures (exchangeable, autoregressive, Toeplitz, etc.) will be considered to reduce the number of fitted parameters, and the final structure will be chosen based on likelihood ratio tests for nested structures and the AIC statistic for non-nested structures. The primary hypothesis will be assessed using a linear contrast at the end of cycle 1. Additional contrasts will be used to assess the difference in fatigue at each time as well as the average difference in fatigue over time.

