**PLEASE COMPLETE AND EMAIL COPY TO HCRN**

## SYNOPSIS

TITLE	A Randomized, Phase II Trial to Evaluate the Efficacy of Supportive Therapy with Ginseng for Patients on Treatment with Regorafenib
SHORT TITLE	Efficacy of Ginseng for Patients on Regorafenib
PHASE	Phase II
OBJECTIVES	
Primary Objective: Assess fatigue with the Multidimensional Fatigue Symptom Inventory-Short Form (MFSI-SF) and Patient-Reported Outcomes Measurement Information System (PROMIS) form for each group (Regorafenib + No Ginseng vs. Regorafenib + Ginseng) to determine if 2000 mg of American Ginseng for 8 weeks has an impact on the fatigue score
 
Secondary Objectives:
 
 
1) Assess the effect of Ginseng on adherence to Regorafenib for CRC subjects with good performance status
 
2) Assess the toxicities of the combination of Regorafenib and Ginseng for CRC subjects with good performance status
 
3) Assess the retention of subjects to the combination of Regorafenib and Ginseng for CRC subjects with good performance status
 
4) Evaluate response rate and overall survival
 

STUDY DESIGN	Randomized
ESTIMATED NUMBER OF SUBJECTS	90: 60 randomized to regorafenib + ginseng and 30 to regorafenib + no ginseng

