#### **5. TREATMENT PLAN**

Regorafenib will be administered 160 mg once daily for the first 21 days of each 28-day cycle. Subjects that randomize to receive Ginseng will take 2,000 mg orally once daily every day for 8 weeks (2 cycles). Subjects that randomize to NOT receive Ginseng will not be given Ginseng. Subjects will be instructed to take regorafenib with a low-fat meal.

Subjects will undergo the fatigue assessments, using the MFSI-SF instrument and PROMIS according to the study calendar. Subjects will have a pill count C2D1 and at the end of treatment visit. Subjects will have the re-staging scan (CT of chest/abdomen/pelvis) at the end of Cycle 2/ week 8 ( $\pm 5$ ). See Study Procedures Manual for questionnaire administration and pill count instructions.

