### **5.2.1 Dose Modifications for Ginseng**

For subjects randomized to receive ginseng there are no dose delays or reductions. If regorafenib is held due to toxicity, the ginseng may continue if the toxicity is attributed to regorafenib only.

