## 7 STUDY SCHEDULE OF EVENTS

Cycle = 28 days

Examination	Screening		Cycle 1		Cycle 2		After completion of Cycle 2	End of Treatment Visit 	Follow up 
	-28 days	-7 days	Day 1	Day 15 (±3)	Day 1 (±3)	Day 15 (±3)	(±5)	30 days (± 7) after last dose of Cycle 2	(±7)
REQUIRED ASSESSMENTS									
Informed Consent	X								
Medical history	X								
Height	X								
Physical examination	X		X	X	X	X		X	
Vital signs including BP, weight and ECOG performance status	X	X 	X	X	X	X		X	
CBC w/ differential		X		X	X	X		X	
Complete Metabolic Profile 		X		X	X	X		X	
PT/INR and aPTT 		X	[D5]		[X]			X	
Pregnancy test 		X							
Urinalysis 		X	X		X				
AEs & concomitant medications	X		X	X	X	X		X	
DISEASE ASSESSMENT									
Pathology Review	X								
CT chest/abdomen/pelvis 	X						X 		
TREATMENT									
Regorafenib 			X	X	X	X			
Ginseng 			X	X	X	X			
OTHER									
MFSI-SF, PROMIS 			X		X 			X	
Pill count 					X			X	
FOLLOW-UP									
For progression, start of additional cancer treatment, and survival									X

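### Section 11 promises a week-8 fatigue score and a contrast at each time, but neither the study calendar nor the visit lists schedule a questionnaire at week 8

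*Combined protocol and SAP*

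**What the plan says.** Section 11, under Analyses: "Subjects will have fatigue assessed at baseline and at weeks 2, 4, and 8". The model is a repeated measures analysis of covariance. On the primary test: "The primary hypothesis will be assessed using a linear contrast at the end of cycle 1". Beyond that: "Additional contrasts will be used to assess the difference in fatigue at each time as well as the average difference in fatigue over time".

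The primary objective, in the synopsis and section 2.1, is "to determine if 2000 mg of American Ginseng for 8 weeks has an impact on the fatigue score".

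On timing, section 5 says: "Subjects will undergo the fatigue assessments, using the MFSI-SF instrument and PROMIS according to the study calendar". The places that schedule questionnaires are:

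- **Section 7, calendar:** Cycle 1 Day 1, Cycle 2 Day 1 and End of Treatment. The column after completion of Cycle 2 is blank for questionnaires.
- **Sections 7.2.1 to 7.2.4 and 7.3, visit lists:** the same three visits plus Cycle 1 Day 15 and Cycle 2 Day 15.
- **Section 7.2.5, 8 weeks (±5 days):** CT and discussion of results, with no questionnaire.

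The calendar places End of Treatment "30 days (± 7) after last dose of Cycle 2". Footnote 7 counts the 30 days from completion of Cycle 2. Section 7.3 makes 30 days a minimum but keeps the ±7 window.

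**The concern.** The analysis plan names three post-baseline times, and the schedule that sites will follow does not collect the last of them. Week 8 is also when the ginseng course named in the objective ends. Patient-reported scores that are not collected cannot be recovered at analysis. If the gap stays, the trial will describe fatigue part-way through the course and again some weeks after it, but not at its end. Section 11 intends the results to inform a follow-up trial, so a missing end-of-course estimate would carry forward into that design.

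**Working it through.** **1. The plan's own figures.** Inputs from section 11: SDs 27.0 and 26.1, 60 and 30 subjects, difference 17, two-sided 0.05.

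- Standard error = √(27.0²/60 + 26.1²/30) = √(12.15 + 22.707) = 5.904. The Satterthwaite df is 59.9 and power from the noncentral t is 80.9%, against 80% stated.
- Half-width = 1.96 × 27.0 × √(1/60 + 1/30) = 11.833, as stated.

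Both reproduce. Neither statement names a visit, so the gap at week 8 does not alter them.

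**2. Nominal days.** Count Cycle 1 Day 1 as day 1, with 28-day cycles and no delay. Section 5.2.1 supports a fixed ginseng end date: "For subjects randomized to receive ginseng there are no dose delays or reductions".

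- Last planned ginseng dose: 8 × 7 = day 56.
- Last planned regorafenib dose: 28 + 21 = day 49.
- Cycle 2 Day 1: day 29 (±3: 26 to 32), which is 56 − 32 = 24 to 56 − 26 = 30 days before day 56.
- Cycle 2 Day 15: day 43 (±3: 40 to 46), which is 56 − 46 = 10 to 56 − 40 = 16 days before day 56.
- 8-week assessment: 56 ± 5 = day 51 to 61.

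**3. Can End of Treatment serve as week 8?** For a completer:

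- Counted from completion of Cycle 2: 56 + 30 ± 7 = day 79 to 93, which is 23 to 37 days after planned ginseng ends.
- Counted from the last regorafenib dose: 49 + 30 ± 7 = day 72 to 86, which is 16 to 30 days after.

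On either count the earliest date is 72 − 56 = 16 days after the last planned ginseng dose and 72 − 61 = 11 days after the 8-week window closes.

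**4. Which named times have data?**

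| Section 11 time | Calendar | Visit lists |
|---|---|---|
| Baseline | yes | yes |
| Week 2 | no | yes |
| Week 4 | yes | yes |
| Week 8 | no | no |

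The visit lists also collect week 6, which section 11 does not mention. Of the three post-baseline contrasts, the calendar supports one and the visit lists two. A model with a separate arm difference at each time cannot estimate that difference where no subject is observed. Interpolating between week 6 and End of Treatment would need a time-trend assumption that the plan does not state, across the stop of ginseng.

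**The case against.** **The primary test is safe.** The contrast that section 11 calls primary is at the end of cycle 1, and both schedules collect that score. A reader might infer that the primary analysis is blocked or underpowered. The documents do not support that; what is lost is one of the additional contrasts.

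**The objective's eight weeks describe the regimen.** The wording sets a duration of ginseng, not an assessment time. A reader might infer that week 8 has to be primary. That is a design choice. An early primary time is defensible, since section 1 reports that most adverse events on regorafenib arise in cycles 1 and 2.

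**The average over time is not lost.** Section 11 does not restrict the average to weeks 2, 4 and 8, so an average over the observed times can be computed. It would not include week 8.

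**The decision bands are not silent on timing.** Two of the three are read at the end of the trial. That phrase names no visit, so it needs defining, but it is not evidence that the bands require week 8.

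**The day counts are nominal.** Regorafenib delays of up to 4 weeks could move Cycle 2 visits. If Cycle 2 Day 15 is counted from the actual Cycle 2 Day 1, its range widens to day 37 to 49, or 7 to 19 days before day 56. Subjects stopping on about day 14 to 38 could have an End of Treatment score between day 51 and 61 if the ±7 window applies to them, but about 30 days off treatment. None of this puts a questionnaire at the 8-week assessment.

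**Other instructions may exist.** Section 11 is itself protocol text, and the Study Procedures Manual, cited for questionnaire administration, was not available. Sites might therefore collect the score. Even so, the calendar and section 7.2.5 should show it.

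**Conclusion.** The discrepancy is real and should be fixed. A broken table does not explain it, because the calendar and the prose of section 7.2.5 agree that week 8 has no questionnaire. As scheduled, there are 0 week-8 scores on either instrument for all 90 planned subjects. The week-8 contrast, and fatigue at the end of the 8-week course, cannot be estimated. The last on-ginseng score is nominally day 29 by the calendar or day 43 by the visit lists, and End of Treatment is at least 16 days past planned ginseng for a completer.

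The loss is confined to additional contrasts and to what can be said about the full course. The week-4 primary contrast, the stated power and the interval width stand. The conclusion assumes that sites follow the calendar and visit lists as written and that the manual adds no week-8 questionnaire. The day counts also assume no cycle delay.

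**What to change.** 1. Add MFSI-SF and PROMIS to the existing 8-week (±5 days) assessment, in both the calendar and section 7.2.5, preferably completed before scan results are discussed. Record the date of the last ginseng dose, since the window runs to day 61, up to 5 days after the last planned dose.
2. Make the calendar, the visit lists and section 11 show the same questionnaire visits, and settle whether weeks 2 and 6 are collected.
3. Keep the primary contrast at the end of cycle 1 unless the sponsor chooses otherwise. State which visit the end of the trial means for the decision bands.
4. Analyse End of Treatment as an off-ginseng follow-up score, not as week 8, and reconcile its timing across the calendar, footnote 7 and section 7.3.

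The cost is amendment wording and one more questionnaire set per subject. Footnote 6 has later surveys completed in clinic, so some subjects may need a clinic contact around the scan. Sample size and stated power do not change.

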### **The secondary objectives are as follows:**

(1) To assess the difference in adherence to regorafenib between the 2 groups. We will assess regorafenib adherence at three times, at the end of the 3rd week of each cycle. Since the recommended dose is once daily for 21 days, a measure of adherence would be the number of pills (out of 21) that each subject takes during each cycle. Using this measure for each subject, we will first compare groups using a 2-sample t-test for cycle 1, cycle 2 and then overall. Next, we will define subjects as being adherent based on having taken their pills on 17 (or more) days out of 21 (i.e. over 80% adherence). Using this definition of adherence, we will fit a 2x2 table comparing adherence rates between groups using a 1 degree of freedom Chi-square test. In addition, the statistician will compare mean daily doses using a t test and median daily doses by using Mann-Whitney test. Our hypothesis for these analyses is that Ginseng will reduce fatigue and thus lead to greater adherence to regorafenib in subjects who are in the Ginseng arm when compared to the no ginseng arm

(2) To assess the difference in toxicities between the two arms. Fisher exact tests will be used to assess the difference in toxicities between the two groups as well as the proportion of subjects

who experience grade 3 or higher toxicities of any kind according to the data safety monitoring plan described below.

(3) To assess the difference in retention between the two arms. As subjects can drop out of the study at various times, we will use Kaplan-Meier methods to estimate the retention distributions in each group and a log-rank test to assess the difference in distributions between the two groups.

(4) Response rate and overall survival are secondary objectives for the trial. Overall survival (OS) as an endpoint is defined in section 8.2.8 of the protocol. OS will be estimated using the Kaplan-Meier method and 90% confidence intervals derived as described in Brookmeyer and Crowley. The median will be provided along with the corresponding 95% CI. Additionally, the 25% and 75% percentiles for these endpoints will also be provided.

Response rate (RR) as an endpoint is defined in section 8.2.5 of the protocol. Objective response (complete response + partial response) rate defined as the proportion of patients who achieve an objective response out of all patients treated on that arm will be estimated along with a 95% confidence interval.

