### 2.2. Secondary Objectives

- 1) Assess the difference in adherence to regorafenib between the two groups. Pill counts will be used to assess adherence. The hypothesis is that Ginseng may increase adherence by decreasing fatigue.
- 2) Assess the difference in toxicities between the two arms.
- 3) Assess the difference in retention between the two arms. Retention is the proportion of subjects who complete the study. Note that they may not completely adhere to the study medication, but as long as they come in for the last measurements, they are considered retained.
- 4) Assess response rate and overall survival

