## 5.1. Study Drug Administration

**Table 1: Study Drug Administration; One cycle is 28 days.**

Drug	Dose	Frequency of administration	Route of administration	Number of cycles
Regorafenib	160 mg	Days 1-21 of each 28-day cycle	Orally	2
Ginseng	1,000 mg	Twice a day (total of 2,000 mg per day) for 4 weeks (28 days)	Orally	2

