### 5.1.1 Treatment Schedules

#### 5.1.1.1 Regorafenib

Regorafenib 160 mg PO once daily will be taken for 3 weeks on/1 week off for 2 cycles. Four 40-mg regorafenib tablets should be taken once a day with approximately 8 fluid ounces (240 mL) of water after a low-fat (<30% fat) meal. Some examples of a low-fat meal are:

- Two slices of white toast with 1 tablespoon of low-fat margarine and 1 tablespoon of jelly and 8 ounces (240 mL) of skim milk (approximately 319 calories and 8.2 g of fat).
- One cup of cereal (i.e. Special K), 8 ounces (240 mL) of skim milk, one piece of toast with jam (no butter or marmalade), apple juice, and one cup of coffee or tea (2 g fat, 17 g protein, 93 g of carbohydrate, 520 calories).

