### **5.2.2 Dose Modifications for Regorafenib**

#### **5.2.2.1 Dose Reduction Levels**

The starting dose of regorafenib is 160 mg once daily. Study medication will be administered on a 3 weeks on/1 week off schedule [3 weeks out of every 4].

Doses will be delayed or reduced for clinically significant hematologic and non-hematologic toxicities that are related to protocol therapy according to the guidelines shown in the Dose Delays/Dose Modifications table that follows. Dose modifications will follow predefined dose levels. Dose adjustments for hematologic toxicity are based on the blood counts obtained in preparation for the day of treatment.

The modifications of regorafenib will follow the following predefined dose levels:		
Dose level 0 (standard starting dose)	160 mg orally every day	Four 40-mg tablets of regorafenib
Dose level - 1	120 mg orally every day	Three 40-mg tablets of regorafenib
Dose level - 2	80 mg orally every day	Two 40-mg tablets of regorafenib

If a subject experiences more than one toxicity, dose reduction should be according to the toxicity with the highest grade.

In the case of two or more toxicities of the same grade, the site investigator may dose reduce according to that deemed most causally related to study treatment.

If more than 2 dose reductions are required, regorafenib only will be discontinued and the rest of the study treatment may be continued. If a dose reduction has been performed, intra-subject dose re-escalation can be considered (up to the maximal 160 mg daily dose) at the discretion of the treating physician, provided that the toxicity(ies) has resolved to baseline.

The following tables outline dose adjustments for toxicities related to study drug except hand-foot skin reaction, hypertension, and liver function test abnormalities.

Recommended dose modification for toxicities except hand-foot-skin reaction, hypertension and ALT/AST/bilirubin			
NCI CTCAE v4.0 a	Dose Interruption	Dose Modification b	Dose for Subsequent Cycles
Grade 0-2	Treat on time	No change	No change
Grade 3	Delay until ≤ Grade 2 c	Reduce by 1 dose level	If toxicity remains < Grade 2, dose re-escalation can be considered at the discretion of the site investigator. If dose is re-escalated and toxicity (≥ Grade 3) recurs, institute permanent dose reduction.
Grade 4	Delay until ≤ Grade 2 c	Reduce by 1 dose level. Permanent discontinuation can be considered at site investigator's discretion.	

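### The regorafenib adherence measure fits neither the four-tablet daily dose nor the pill-count schedule, and the nominal cycle-2 count falls after opened bottles are due for discard

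*Combined protocol and SAP*

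**What the plan says.** Section 2.2 names the tool: "Pill counts will be used to assess adherence". Section 11, secondary objective (1), gives the measure: "a measure of adherence would be the number of pills (out of 21) that each subject takes during each cycle". The same paragraph calls a subject adherent if doses were taken on at least 17 of the 21 days. It places the assessment at three times, each at the end of week 3 of a cycle, and plans t-tests for cycle 1, cycle 2 and overall.

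The rest of the protocol describes something different.

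- **Dosing.** Table 1 in Section 5.1 gives regorafenib on "Days 1-21 of each 28-day cycle" for two cycles. Section 5.1.1.1 says "Four 40-mg regorafenib tablets should be taken once a day", and that it "will be taken for 3 weeks on/1 week off for 2 cycles". The first reduced level in Section 5.2.2.1 is "Three 40-mg tablets of regorafenib" and the second is two tablets.
- **Counts.** Section 5 says "Subjects will have a pill count C2D1 and at the end of treatment visit". The Section 7 schedule and Sections 7.2.3 and 7.3 agree. Footnote 6 has the subject bring the bottle to the visit.
- **Timing of the last count.** The Section 7 schedule and Section 7.3 place End of Treatment 30 days (±7) after the last dose of Cycle 2. Footnote 7 places it 30 days after Cycle 2 is completed or, for early stoppers, 30 days after discontinuation.
- **Discard.** Storage and Handling, under Section 9.2, has unused tablets discarded 28 days after a bottle is opened.
- **Instructions elsewhere.** Section 5 adds: "See Study Procedures Manual for questionnaire administration and pill count instructions". That manual is not part of the documents reviewed.

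**The concern.** Section 11 cannot be carried out as written. It scores pills out of 21 when a full cycle is four times that many tablets. It asks for three assessments where two cycles and two counts exist. It also relies on a cycle-2 count scheduled for a day when every opened bottle should already have been discarded.

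Adherence is the first secondary objective and part of the trial's hypothesis, and Section 11 says the adherence estimates can help size a later trial. Cycle 2 is one of the three planned t-test comparisons and half of the overall measure. A pill count infers doses taken from tablets left over, so leftovers that disappear before they are counted make use look better than it was.

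**Working it through.** **The plan's own figure.** 17/21 = 81.0% and 16/21 = 76.2%, so 17 is the smallest number of days above 80%. The cut-off is correct in days.

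**Unit.** Tablets per cycle = tablets per day × 21 (Sections 5.1.1.1 and 5.2.2.1).

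| Tablets per day | Full cycle | 17 days |
|---|---|---|
| 4 | 84 | 68 |
| 3 | 63 | 51 |
| 2 | 42 | 34 |

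Only daily doses number 21; 21 tablets at four a day would last 5.25 days. The conversion must use the dose level in force. A fixed division by four, which no section proposes, would turn 63 tablets into 15.75 days and 42 into 10.5, although both are 21 full days at the reduced level.

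A change of level within a cycle adds an ambiguity. As an illustration, take 7 days prescribed at four tablets and 14 at three: 7×4 + 14×3 = 70. A count of 54 taken fits

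- 3×4 + 14×3 = 54, which is 17 days (adherent), or
- 6×4 + 10×3 = 54, which is 16 days (not adherent).

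A count of 55 has the same problem: 4×4 + 13×3 (17 days) or 7×4 + 9×3 (16 days). In this example no other count straddles the cut-off.

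**Number of assessments.** Two cycles with one count each give two, against three in Section 11. For cycle 1 the later date does no harm: days 22 to 28 are off regorafenib, so with on-schedule dosing the Cycle 2 Day 1 count equals a week-3 count.

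**Cycle-2 count against the discard limit.** Write C2D*n* for day *n* of Cycle 2. If the last dose is on day L, no bottle in use was opened after L, so every limit falls by L + 28. The nominal visit is at L + 30 or later. This covers early stoppers too.

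For a subject dosed on schedule, L = C2D21:

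- Latest possible limit: 21 + 28 = C2D49.
- Visit counted from that last dose: 21 + 30 = C2D51, which is 51 − 49 = 2 days late.
- Visit counted from completion of Cycle 2: 28 + 30 = C2D58, which is 58 − 49 = 9 days late.
- With the ±7 window, the first visit runs from C2D44 to C2D58. It can be in time only if held by C2D49, and only for a bottle opened on C2D16 or later (44 − 28 = 16). The second runs from C2D51 to C2D65 and never can be.

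**Week-8 contact (Section 7.2.5).** This is nominally C2D28. A bottle opened in cycle 2 has a limit no earlier than 1 + 28 = C2D29, so the nominal contact precedes them all. Bottles hold 30 tablets (Section 9.2); at four a day fresh bottles open on days 1, 8 and 16, with limits C2D29, C2D36 and C2D44. Within the ±5 window (C2D23 to C2D33) only the first limit can be overrun, and at full dosing that bottle is empty by C2D8.

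**The case against.** The case on the other side is that most of this is wording. Section 11 itself speaks of once-daily dosing and of days out of 21, and footnote 6 refers to doses, so the intended unit is clear. The three assessments may loosely mean cycle 1, cycle 2 and overall. The Study Procedures Manual may hold the conversion. The mid-cycle ambiguity affects only two counts in one constructed schedule. The discard instruction does not say tablets are thrown away uncounted, and Section 9.2 requires records of disposition and return. Upward bias needs two further steps: discard without a record, and then treating absent tablets as taken. Both arms share the same discard rule, and no effect on the between-arm difference has been estimated.

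Much of this stands. The unit and the number of assessments would be near-clerical on their own. The ambiguity is narrow, the manual could close the conversion gap, and loss of the cycle-2 count is not certain. What does not fall away is that the visit timing and the discard instruction, each followed as written, put the count after the tablets are due to be gone. A shared rule does not by itself protect the comparison: the arm with more missed doses has more leftovers to lose, so the difference could shrink.

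One further point stands. The hand-foot-skin table in Section 5.2.2 has interruptions of at least 7 days. One lying wholly within days 1 to 21 leaves at most 14 dosing days, below 17 without any non-adherence. Section 11 does not say how such days count.

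**Conclusion.** The concern holds and should be fixed. The 21 and the 17-day cut-off are right as daily doses; the word for the unit, the number of assessments and the timing of the cycle-2 count are not consistent with the rest of the protocol. At the nominal End of Treatment visit every opened bottle is past its limit, by 2 to 9 days at the least for a subject whose last regorafenib dose is on C2D21, and by at least 2 days for early stoppers. Unopened bottles are unaffected.

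The mismatches rest on the text and arithmetic alone. A lost or overstated cycle-2 count also requires that leftovers go uncounted, which the accountability records may prevent. The size of any bias cannot be worked out from the documents. The primary fatigue analysis and the sample size are unchanged.

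**What to change.** 1. In Section 11, define adherence as daily doses taken out of 21, derived from tablets taken and the dated prescribed tablets per day, summed over segments when the level changes within a cycle. Count leftovers at the contact where the level changes, or state in advance how a shortfall is apportioned if no count was made then. Keep the 17-of-21 cut-off, and state how days held under the protocol are counted. If the Study Procedures Manual already has a conversion, cite it.
2. Replace the three week-3 assessments with cycle 1 (from the Cycle 2 Day 1 count), cycle 2 and overall, matching the planned t-tests.
3. Take the cycle-2 count at the existing week-8 contact. For early stoppers, or if that contact is missed, count and record leftovers before disposal.
4. Reconcile Section 5, the Section 7 schedule and footnote 7, Section 7.3, Storage and Handling, and Section 11. None of this requires a change to a dose or to the discard instruction.

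The cost is wording, one count moved to a contact that now lists only a CT and physician follow-up, and a bottle check there and at a dose change. Dose-level data are already needed for the planned mean-daily-dose comparison. No extra subjects or visits are required.
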